Nicotine Replacement Therapy (NRT) helps combat nicotine withdrawal symptoms by providing users with nicotine in long-acting (patch) or short-acting (mask gum, lozenges, inhaler, nasal spray) form. Use of NRT in any form increases smoking abstinence by 60% compared to placebo (RR 1.60, 95% CI 1.53–1.68). To increase effectiveness, the nicotine patch can be combined with short-acting NRT, which is more effective than using a form of NRT (RR 1.34, 95% CI 1.18–1.51) (10). Bupropion increases norepinephrine and dopamine levels and is approved as an antidepressant for smoking cessation. Increases smoking cessation rates compared to placebo (OR 1.75, 95% CI 1.52 to 2.01) (8.9). Varenicline is a partial nicotinic receptor agonist that doubles smoking abstinence rates compared to placebo (RR 2.24, 95% CI 2.06–2.43). (10) These results have been obtained in smokers treated on an outpatient basis. The study of the effectiveness of these different treatments in hospitalized subjects has been little and marginally analyzed.(6) Among the studies carried out, it shows that hospitalized subjects who received treatment for smoking cessation and support had abstinence rates greater than 6 months. The analysis carried out in this study does not differentiate by type of pharmacological treatment. The predominant pharmacological treatment was NRT. (11) Smoking cessation in hospitalized patients has been associated with lower rates of postsurgical complications, better tissue healing and proliferation, and reversibility of the attenuation of inflammation mechanisms. (12,13)

Hospitalization is a vital scenario to address tobacco consumption for various reasons and benefits; among the most important are the prohibition of smoking on the hospital premises and the special availability for quitting that the smoker has during admission to a hospital admission promotes subsequent tobacco cessation because a severe illness, primarily if related to tobacco, can increase smokers' motivation to quit.

MAIN OBJECTIVE

Our objective will be to analyze the effectiveness of the combination of bupropion and nicotine versus nicotine replacement therapy to quit smoking in hospitalized subjects 12 months after discharge.

SPECIFIC OBJECTIVES

1. Analyze the effectiveness of the combination of pharmacological therapies to quit smoking in hospitalized subjects 3, 6 and 12 months after discharge.
2. Evaluate the symptoms and signs of withdrawal in the different groups throughout their follow-up.

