(14)

-Acute or chronic lung disease: Acute or chronic lung disease will be considered by medical diagnosis.

-Exhaled carbon monoxide: a value greater than or equal to 7 ppb is defined as positive (subject with active smoking).

-Cotinine in urine: defined as positive (subject with active smoking) positive test (qualitative test)

-Nicotine dependence (Fagerström Questionnaire): mild, moderate and severe.

-Withdrawal symptoms questionnaire.

-Nicotine Craving Questionnaire (Urge to smoke, understood as a physiological and motivational state that drives the desire to smoke tobacco).

-Adverse reactions questionnaire.

-Respiratory symptoms questionnaires (PLATINO).

-Pulmonary function tests (pre- and post-bronchodilator spirometry, carbon monoxide diffusion, and 6-minute walk)

-Beck Anxiety and Depression Questionnaires.

Procedures for collecting information using instruments and data quality control methods.

Data Capture.

a)

b) 1-Subject identification (inclusion/exclusion criteria)

c) 2-Signature of informed consent

d) 3-Randomization of the drug (2 groups: a-nicotine patches, b-combination: nicotine patches + bupropion)

e) 4-Start hospitalization treatment

f) - Processes: Medications are given in a personalized way during hospitalization; brief advice is given, and questionnaires and measurements of exhaled CO and cotinine in urine are performed (treatment start day is day 0). The pharmacological treatment given to the subject will be for at least 12 weeks.

g) 5-Monitoring during hospitalization to provide medications

- h) 6-Upon discharge, an appointment is made at the Smoking Clinic within the first 14 days of discharge, and anti-smoking treatment for home use and brief advice will be provided.
- i) 7-First appointment at the Smoking Clinic
- j) - Processes: brief advice; intake of exhaled CO and cotinine in urine). It is scheduled to begin cognitive behavioral therapy (CBT) in a group, which lasts ten sessions, two times a week, with mixed modality (online or in-person).
- k) 8-Start CBT in the next two weeks after discharge.
- l) 9- Second appointment at the Smoking Clinic at the end of therapy (3 months after discharge)
- m) - Processes: brief advice; questionnaires and measurement of exhaled CO and cotinine in urine are performed; pre- and post-bronchodilator spirometry, carbon monoxide diffusion, 6-minute walk.
- n) 10-Third appointment at the Smoking Clinic 6 months after discharge:

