- o) - Processes: brief advice; questionnaires and measurement of exhaled CO and cotinine in urine are performed; pre- and post-bronchodilator spirometry, carbon monoxide diffusion, 6-minute walk)
- p) 11-Fourth appointment at the Smoking Clinic 12 months after discharge
- q) - Processes: brief advice; questionnaires and measurement of exhaled CO and cotinine in urine are performed; pre- and post-bronchodilator spirometry, carbon monoxide diffusion, 6-minute walk)
- r) The information collection will be carried out through the INER RedCAP platform, which has security mechanisms for the data obtained and methods for adequate control. The protocol researchers will carry out data capture.

Results analysis plan.

1- A retrospective analysis was carried out on hospitalized patients with a history of active smoking, with the following characteristics: 40% of the patients evaluated had low dependence on nicotine, and 60% had moderate and severe dependence. Of the patients evaluated, 72% were male, and 28% were female. Proportional allocation is carried out for stratified sampling, Stratified randomization for sex (man and woman), and for low and moderate/severe dependence

2- Statistical analysis methods according to the type of variables: the variables will be analyzed according to their type of distribution and whether they are quantitative or qualitative, by student's t or chi2 as appropriate. A descriptive analysis will be carried out on each of the variables. Subsequently, a comparative analysis will be carried out between the 2 groups included, using ANOVA or Kruskal Wallis, depending on their distribution. The analysis of the main objective will be carried out by intention to treat according to the treatment granted and randomization. Randomization was stratified by level of nicotine dependence and sex. There will be no blinding. The primary outcome will be abstinence at 12 months, and its association with the randomized treatment group will be seen. As a complementary analysis, a per-protocol analysis will be performed according to the treatment received. Finally, through multivariate analysis by logistic regression, abstinence or non-abstinence at one year was analyzed depending on the treatment received, adjusted for the different covariates such as sex, age, smoking rate, and level of dependence.

3-The statistical analysis will be carried out using the STATA V13 statistical package.

ETHICAL CONSIDERATIONS

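### Repeated withdrawal, craving and Beck scores have only unadjusted two-group tests named for them; a model using the day-0 score and the strata would be more precise at little cost

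*Combined protocol and SAP*

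**What the plan says.** Specific objective 2 is longitudinal and comparative: "Evaluate the symptoms and signs of withdrawal in the different groups throughout their follow-up". The list of study variables includes a withdrawal questionnaire, a craving questionnaire and the Beck anxiety and depression questionnaires.

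Under Data Capture, at the start of treatment in hospital (step 4), "questionnaires and measurements of exhaled CO and cotinine in urine are performed (treatment start day is day 0". Questionnaires are listed again at three later visits: "Second appointment at the Smoking Clinic at the end of therapy (3 months after discharge", "Third appointment at the Smoking Clinic 6 months after discharge" and "Fourth appointment at the Smoking Clinic 12 months after discharge".

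Results analysis plan, item 2, chooses a test by distribution and by whether variables are quantitative or qualitative: "whether they are quantitative or qualitative, by student's t or chi2 as appropriate". After a descriptive analysis, "a comparative analysis will be carried out between the 2 groups included, using ANOVA or Kruskal Wallis, depending on their distribution". The only adjusted model is the logistic regression, in which "abstinence or non-abstinence at one year was analyzed depending on the treatment received, adjusted for the different covariates such as sex, age, smoking rate"; dependence is a further covariate. Randomisation is stratified by sex and by low versus moderate/severe dependence, and the trial is unblinded.

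**The concern.** A symptom score measured before treatment often carries information about the same patient's later score. If it does here, a comparison that leaves it out carries avoidable noise. The same holds for sex and dependence: the design stratifies on them, but the named score comparisons do not use them.

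There is also a gap between question and method. Objective 2 concerns the course of symptoms over follow-up. With two groups, ANOVA is the t test and Kruskal-Wallis is the rank-sum test. Neither estimates whether the difference between arms changes from 3 to 12 months, and the rank test alone gives a p-value without a difference on the score's scale.

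At stake are the width of the intervals on secondary outcomes in a small trial, and a choice of adjustment left open until unblinded data are in hand.

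**Working it through.** **Schedule against method**

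| Time | Questionnaires listed? | Method named for the scores |
|---|---|---|
| Day 0 | yes | no role in any score comparison |
| First clinic appointment, within 14 days of discharge | no (advice, CO and cotinine only) | none |
| 3, 6 and 12 months | yes, each | t test, ANOVA or Kruskal-Wallis; no visit or covariate named |

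**Inputs**
- Evaluable patients: 50 per group (Sample size). The documents give no SD, target difference or correlation for any score, so there is no planned figure for the scores to reproduce.
- The loss step does reproduce: 50/(1 − 0.25) = 66.7, so 67 per group. The 50 itself does not follow from 65% versus 80%, one-sided 5% and 80% power, for which the usual two-proportion formula gives 109 per group. That is a separate matter. Here 50 only puts the gain in terms of patients; it cancels out of the percentage cuts.
- Correlation r between the day-0 and follow-up score: assumed, 0.2 to 0.7.
- For detectable differences: two-sided 5% and 80% power, my convention for these scores.

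**Formulas**
- Variance of the difference in means: unadjusted 2·SD²/n; with linear baseline adjustment 2·SD²(1 − r²)/n. The ratio is 1 − r².
- Effective n per group = 50/(1 − r²).
- Detectable difference = (1.960 + 0.842) × √(2(1 − r²)/50) SD. At r = 0 this is 2.802 × 0.2 = 0.56 SD.

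| r | 1 − r² | Variance cut | Standard error cut | Effective n per group | Detectable difference (SD) |
|---|---|---|---|---|---|
| 0 | 1.00 | 0% | 0% | 50 | 0.56 |
| 0.2 | 0.96 | 4% | 2% | 52 | 0.55 |
| 0.3 | 0.91 | 9% | 5% | 55 | 0.53 |
| 0.5 | 0.75 | 25% | 13% | 67 | 0.49 |
| 0.7 | 0.51 | 49% | 29% | 98 | 0.40 |

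At r = 0.5 the gain equals about 17 patients per group (66.7 − 50).

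**Why not a change score.** Its variance relative to the follow-up score alone is 2(1 − r): 1.6, 1.4, 1.0 and 0.6 at r = 0.2, 0.3, 0.5 and 0.7. It loses precision whenever r is below 0.5. Using baseline as a covariate avoids that.

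**Is day 0 a clean baseline?** Data Capture puts randomisation at step 3 and the day-0 questionnaires at step 4, in the same line as giving the medication. In an open-label trial the patient could know the arm, or have had a first dose, when answering. The documents do not settle the order. Sex and dependence do not raise this question, because stratified randomisation needs both beforehand.

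**The case against.** The strongest reply is that randomisation makes the unadjusted tests valid, the outcomes are secondary, and the gain depends on a correlation that nobody has stated. All of that stands. Day 0 is an inpatient assessment and the follow-ups are months after discharge, so r may be low; at 0.2 the variance gain is only 4%. The 1 − r² formula describes linear adjustment and does not directly measure a gain over Kruskal-Wallis. The plan allows for non-normal scores, and a replacement model must too.

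Several stronger readings are tempting but unsupported:
- *The plan commits to single-visit tests on those present and rules out adjustment.* It names test families and is silent on visits, covariates and missing scores. It forbids nothing.
- *Visit-by-visit tests throw away the earlier data of patients lost later.* They do not: a patient lost after month 3 still counts in a month-3 test. What separate tests miss is the use of earlier visits to inform later contrasts. The 25% loss has no stated timing, so that benefit cannot be sized.
- *Every form is certainly given at every listed visit.* The visit lines say only questionnaires. That the withdrawal, craving and Beck forms are included is the natural reading, but it is an inference.
- *Lung function is affected in the same way.* No day-0 spirometry, diffusion or walk test is listed, so the baseline argument does not extend to it.

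No listed objective names craving or Beck scores. The case is firmest for withdrawal, and applies to the others only if they are compared between arms.

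That adjustment is not forbidden does not answer the point. Leaving it open in an unblinded trial invites a choice made after the data are seen.

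**Conclusion.** The point holds as an inexpensive improvement in precision on secondary scores. It shows no bias and does not touch the primary abstinence analysis. A better method exists for data that the protocol appears already to collect, and it fits objective 2 more closely than the tests named.

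The gain in variance is r²: slight at r of 0.2 to 0.3 and material from about 0.5. It rests on three assumptions: the value of r, that the forms are given at day 0 and at the later visits, and that the day-0 answers are unaffected by knowledge of the arm or by treatment.

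**What to change.** In Results analysis plan, item 2, specify for the withdrawal score (and for craving and Beck scores if they are compared between arms):

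- One linear mixed model for the 3-, 6- and 12-month values, allowing for correlation within patient, with randomised arm, visit, arm by visit, day-0 score, sex and dependence stratum.
- Adjusted mean differences with 95% CIs at each visit. Keep the unadjusted tests as descriptive.
- If scores are clearly skewed, a transformation or robust or bootstrap standard errors.

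In Data Capture, say which questionnaires are given at which visit. State that the day-0 forms are completed before the allocation is disclosed and before the first dose. Where that was not done, adjust only for sex and dependence stratum.

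The model also lets earlier visits inform later contrasts for patients lost to follow-up, provided that loss depends only on what has been observed. The cost is a little more analysis work and reliance on model assumptions. No new data are needed.

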3. Record the adverse effects of the different pharmacological therapies reported in the different groups throughout their follow-up.
4. Evaluate the lung function of the different groups at 3 months after discharge, 6 months and 12 months after discharge.

METHODS

a) Location of the study.

National Institute of Respiratory Diseases, Ismael Cosío Villegas México.

Smoking and COPD Research Department.

b) Description of the population:

Inclusion criteria:

1. Over 18 years of age.
2. Active smokers (smoking more than 100 cigarettes in their entire life and having consumed cigarettes in the last 30 days)
3. Hospitalized subjects with acute or chronic lung disease.
4. Signing of informed consent.

Exclusion criteria:

1. Subjects with pharmacological treatment to stop smoking during recruitment or in the last month.
2. Contraindications to the use of pharmacological therapy. (Annex is attached the contraindications for the use of medications)
3. Subjects who cannot maintain follow-up.

Elimination criteria:

1. In an analysis by intention to treat, there will be no elimination of subjects after randomization.

Sample size:

The sample size calculation is carried out by difference between proportions, with a confidence level of 95%, power of 80%, unilateral, with an observed proportion of 65% and an expected proportion of 80% for the combination of pharmacological therapy; 50 subjects are required for each group; If a loss of participants is estimated at 25%, 67 subjects are required for each group. The sample size was carried out in the WinEpi 2006 program.

c) Outcome variables and description of other study variables.

Outcome variable:

-Abstinence: abstinence from tobacco is defined as its suspension 12 months after hospital discharge, corroborated by detection of exhaled carbon monoxide less than 7 ppb and/or detection of cotinine in urine (positive).

-Active smoker: defined as an active smoker who has consumed more than 100 cigarettes in his or her entire life and who has consumed cigarettes in the last 30 days.

-CBT (cognitive behavioral therapy) is a model for treating problematic behaviors that focuses primarily on identifying and changing maladaptive patterns of behavior and thoughts, including problem-solving and coping skills rooted in relapse prevention theory, along with the cognitive restoration of maladaptive thoughts to regulate emotions and is combined with the recommendations of the Clinical Practice Guideline (CPG) for tobacco.

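### Lung function is measured at three visits but compared one visit at a time; a mixed model using all visits would handle the expected 25% loss better (minor, secondary objective)

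*Combined protocol and SAP*

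**What the plan says.** Specific objective 4 is to "Evaluate the lung function of the different groups at 3 months after discharge, 6 months and 12 months after discharge". The outcome section lists the measures: "Pulmonary function tests (pre- and post-bronchodilator spirometry, carbon monoxide diffusion, and 6-minute walk". Under Data Capture, all of them are done at the second, third and fourth clinic appointments (3, 6 and 12 months). The in-hospital step lists questionnaires, exhaled CO and cotinine, but no lung-function test.

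Item 2 of the Results analysis plan gives one general rule for all variables. They are analysed according to distribution and "whether they are quantitative or qualitative, by student's t or chi2 as appropriate". After a descriptive analysis, "a comparative analysis will be carried out between the 2 groups included, using ANOVA or Kruskal Wallis, depending on their distribution". Lung function is not named. The logistic regression concerns abstinence only. No repeated-measures model, missing-data rule or analysis set is given for objective 4.

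On losses, the Sample size section says "If a loss of participants is estimated at 25"%, 67 per group are needed. On the analysis set, the Elimination criteria say "In an analysis by intention to treat, there will be no elimination of subjects after randomization", and item 2 says "The analysis of the main objective will be carried out by intention to treat according to the treatment granted and randomization".

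**The concern.** Student's t, one-way ANOVA and Kruskal-Wallis are tests at a single time point. A patient measured at 3 and 6 months who is absent at 12 months adds nothing to the 12-month comparison, although the two earlier values are in the database and are probably correlated with the missing one.

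Two things are at stake. The first is precision, which is lost even when losses are random. The second is bias. The patients are inpatients with lung disease, and those in poor respiratory health may be the ones who stop attending. The trial is unblinded and only one arm takes bupropion, so the pattern of loss could differ by arm. If it does, the 12-month comparison of attenders is distorted in a way that the earlier visits could partly correct.

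**Working it through.** **The plan's own figures.** 50 / (1 - 0.25) = 66.7, so 67 per group, as stated. At 12 months, 67 × 0.75 = 50.25, so about 50 per group are measured and about 17 are not. (Whether 50 is the right number for the abstinence comparison is a separate question, on which nothing here depends.)

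**Assumptions not in the documents.** Cumulative losses of 8% at 3 months and 17% at 6 months (only the final 25% is the plan's), no return after a missed visit, an equal correlation ρ between any two visits of 0.5, 0.7 or 0.9, and no true difference. Results are in SD units.

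**1. Precision under random loss.** Numbers measured per arm: n3 = 67 × 0.92 = 61.6, n6 = 67 × 0.83 = 55.6, n12 = 67 × 0.75 = 50.25.

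- Attenders only: SE = √(2 / 50.25) = 0.200.
- All visits, large-sample likelihood result for monotone loss: SE = √{2 [R1/n3 + (R2 - R1)/n6 + (1 - R2)/n12]}. Here R1 = ρ² is the share of 12-month variance explained by month 3, and R2 = 2ρ²/(1 + ρ) is the share explained by months 3 and 6.

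| ρ | R1 | R2 | SE, all visits | Reduction from 0.200 |
|---|---|---|---|---|
| 0.5 | 0.25 | 0.333 | 0.194 | about 3% |
| 0.7 | 0.49 | 0.576 | 0.189 | about 5% |
| 0.9 | 0.81 | 0.853 | 0.184 | about 8% |

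Repeated simulations (3000 trials per setting) agree: the reductions ran from about 2% at ρ = 0.5 to about 9% at ρ = 0.9.

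**2. Bias when loss depends on lung function in one arm only.** After month 3, the log-odds of loss in that arm change by -1 per SD of the previous visit's value, with the intercept set so that total loss stays at 25%. Loss in the other arm is random. The error rate is P(|Z + bias/SE| > 1.96) with SE = 0.20.

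| ρ | Bias, attenders only | Bias/SE | Two-sided error (nominal 5%) |
|---|---|---|---|
| 0.5 | 0.08 | 0.40 | about 7% |
| 0.7 | 0.12 | 0.60 | about 9% |
| 0.9 | 0.15 | 0.75 | about 12% |

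The all-visit estimate is nearly unbiased here, because the loss is driven by values that it uses.

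**3. Sensitivity to the assumption.**

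- Same dependence in both arms: no bias and an error of 5%.
- Slope -0.5 in one arm: bias 0.05 to 0.08 SD, error 6% to 7%.
- Slope -1 in one arm, with loss there rising to about 30%: bias about 0.11 to 0.19 SD, error about 8% to 15%.

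**The case against.** **The plan is silent rather than wrong.** It gives a general rule and never names lung function. Objective 4 states no hypothesis, contrast or key time point, and it is the last of four specific objectives. A stated missing-data rule with a sensitivity analysis would also be defensible. This stands as a reason to rate the point as minor. It does not remove it: the general rule is the only one that reaches these variables, and it does not use the repeated measurements.

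**The bias rests on an assumption.** No figure in the documents supports loss that depends on lung function in one arm only, and under equal dependence the bias vanishes. This stands. The precision gain does not need that assumption, but it is small.

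**The remedy is partial.** The near-zero bias of the all-visit estimate follows from letting loss depend on a recorded earlier value. With no in-hospital test listed, loss before month 3 has nothing to condition on. In simulation the all-visit estimate was biased by 0.04 to 0.07 SD when early loss also depended on the unmeasured in-hospital value, and by 0.09 to 0.11 SD when loss depended on current lung function. This also stands. The mixed model was still never materially worse than the comparison of attenders in these runs.

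**Two stronger readings that the documents do not support.** A reader might see a breach of the plan's statement that "there will be no elimination of subjects after randomization". That sentence opens with a condition, an intention-to-treat analysis, and item 2 assigns intention to treat to the main objective, which is abstinence. For objective 4 the analysis set is unstated, so there is no contradiction. A reader might also infer that anyone who misses a visit is dropped altogether. A visit-by-visit test leaves a patient out only at the missed visit. Complete exclusion would need a complete-case repeated-measures ANOVA, which the plan does not specify.

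**Conclusion.** The point holds as a minor improvement to a secondary objective. The named tests use only those measured at each visit, and at the plan's own 25% loss the 12-month comparison rests on about 50 of 67 patients per arm. Using all visits would cut the 12-month standard error by about 2% to 9% under random loss, given the assumed loss pattern and correlations of 0.5 to 0.9.

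Bias is possible but not shown. It is about 0.08 to 0.15 SD, with a two-sided error of about 7% to 12%, if loss depends on the previous value in one arm only at the assumed slope with total loss held at 25%. It is zero if the dependence is equal in both arms. It would be wrong to conclude from the documents that the comparison of attenders is biased, or to quote the larger figures without saying that they need about 30% loss in the affected arm.

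**What to change.** In item 2 of the Results analysis plan, replace the visit-by-visit tests for each continuous lung-function measure with one linear mixed model. It should use every available 3-, 6- and 12-month value by randomised arm, with arm, visit, arm-by-visit, sex and dependence stratum as fixed effects and an unstructured within-patient covariance. Report the arm difference with its confidence interval at each visit, and tabulate deaths and missed visits by arm beside it.

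The cost is wording: no new visits, data or patients, and the Stata 13 package that the plan names fits the model with its mixed command. The plan should state the limits. The model assumes that losses are explained by earlier recorded values, it implicitly projects values beyond death, and it cannot correct loss before month 3. Patients who attend none of the three visits still contribute nothing.

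### Randomisation is stratified by sex and nicotine dependence, but no planned comparison by randomised arm uses those strata; adding them is a small, almost free improvement

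*Combined protocol and SAP*

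**What the plan says.** - **Design.** Results analysis plan, item 1, sets two stratification factors: sex, and dependence split into low versus moderate/severe. Item 2 confirms it: "Randomization was stratified by level of nicotine dependence and sex". This gives four strata across two arms ("2 groups: a-nicotine patches, b-combination: nicotine patches + bupropion").
- **Primary comparison.** Item 2 calls for intention to treat and then says: "The primary outcome will be abstinence at 12 months, and its association with the randomized treatment group will be seen". It names no test, effect measure, confidence interval or adjustment.
- **Tests listed.** Variables are to be analysed "by student's t or chi2 as appropriate", with ANOVA or Kruskal-Wallis for the comparison between groups. Of these, only chi2 suits a binary outcome in two arms.
- **Adjusted model.** The last analysis in item 2, after the per-protocol analysis, is a logistic regression of one-year abstinence on treatment received, with sex, age, smoking rate and dependence as covariates.
- **Sizing.** The Sample size paragraph works "with a confidence level of 95%, power of 80%, unilateral". It sets 65% abstinence against 80% under the combination, and reaches 50 per group, or 67 after allowing for loss.

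**The concern.** Balancing the arms within strata removes between-stratum variation from the treatment difference. A pooled chi2 still counts that variation in its standard error. If the strata predict the outcome, the test is then somewhat conservative, a risk-difference interval built the same way is somewhat too wide, and part of what stratification bought is not used. The one model that holds both factors is not a comparison of the randomised arms, so it does not fill the gap. This trial has little power to spare.

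**Working it through.** **1. The plan's own figure.** Inputs from the Sample size paragraph: 65% versus 80%, one-sided 5%, power 80%.

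Two groups, pooled variance under the null, with mean rate 0.725:
n = [1.645 × √(2 × 0.725 × 0.275) + 0.842 × √(0.65 × 0.35 + 0.80 × 0.20)]² / 0.15² ≈ 108.5, so 109 per group.

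The plan says "50 subjects are required for each group". Continuity correction (122), unpooled variance (107) and arcsine (108) do not give 50 either. A one-sample formula with null 80% and alternative 65% does: [1.645 × √0.16 + 0.842 × √0.2275]² / 0.0225 = 49.9. The allowance for loss reproduces: 50 / 0.75 = 67. By formula, one-sided power is 51% at 50 per group and 62% at 67. This is a separate matter, but it sets the scale for what follows.

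**2. Strata.** Item 1 gives 72/28 for sex and 40/60 for dependence. Taking the two as independent (an assumption), the shares are 0.288, 0.432, 0.112 and 0.168, or about 39, 58, 15 and 23 of 134 patients after rounding.

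**3. Prognostic strength.** The documents give no abstinence rates by stratum, so the odds ratios for sex and dependence are assumptions, varied from 1/1 to 2/4.

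**4. Methods compared.**
- Crude: z = (p1 − p0) / √[p(1 − p)(1/n1 + 1/n0)].
- Cochran-Mantel-Haenszel (CMH): z = Σ(y1j − n1j·mj/tj) / √Σ[n1j·n0j·mj(tj − mj) / (tj²(tj − 1))]. In stratum j, y1j is the number abstinent in the combination arm, n1j and n0j are the arm sizes, mj is the total abstinent and tj is the total number of patients.

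There were 40,000 simulated trials per scenario with 67 per group, near 1:1 balance within strata and no continuity correction. Entries are crude / CMH, in percent.

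| Odds ratios sex/dependence | Power, one-sided 5% | Power, two-sided 5% | Type I error, one-sided |
|---|---|---|---|
| 1 / 1 | 62.8 / 62.5 | 49.8 / 49.6 | 4.9 / 4.8 |
| 1.3 / 1.5 | 63.0 / 63.1 | 50.2 / 50.4 | 5.0 / 5.0 |
| 1.5 / 2 | 62.8 / 63.3 | 49.9 / 50.8 | 4.8 / 5.0 |
| 1.5 / 3 | 63.1 / 64.6 | 50.2 / 52.1 | 4.6 / 5.1 |
| 2 / 4 | 63.2 / 65.7 | 49.8 / 53.3 | 4.1 / 5.0 |

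A second simulation at 2/4 gave 63.3 / 65.9 one-sided and 50.5 / 53.5 two-sided. The mean 95% half-width for the risk difference, crude versus stratified, is 14.8 versus 14.8 points at 1/1, 14.8 versus 14.6 at 1.5/2, and 14.8 versus 14.2 at 2/4.

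At 50 per group the one-sided powers are 52.4 / 51.8 at 1/1 and 52.4 / 54.8 at 2/4.

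**5. Hand check at 2/4 under no treatment effect.** The stratum rates are 0.85, 0.59, 0.74 and 0.41, with weighted mean 0.651. Between-stratum variance: 0.288 × 0.199² + 0.432 × 0.061² + 0.112 × 0.089² + 0.168 × 0.241² ≈ 0.0237. Total variance: 0.65 × 0.35 = 0.2275. Share: 0.0237 / 0.2275 ≈ 10.4%. With balanced strata the true standard error is √(1 − 0.104) ≈ 0.947 of the crude one. The crude one-sided error is then P(Z > 1.645 / 0.947) ≈ 4.1%, which agrees with the simulation.

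**6. Without balance inside strata.** With simple 1:1 allocation inside each stratum, the crude type I error is about 5.0% to 5.2% at 2/4, so the conservatism disappears. Two-sided power, crude versus CMH, is then 50.3% versus 52.5% at 2/4 and 49.6% versus 49.0% at 1.3/1.5.

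**The case against.** The strongest reply is that the plan never prescribes a crude chi2 for the primary outcome. That stands: chi2 is the likely reading, not a stated choice. What can be read directly is that no stratified or adjusted comparison by randomised arm is named.

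Second, the loss depends on facts that the documents do not give: how far sex and dependence predict abstinence, and whether blocking or a similar method balances the arms within strata. This also stands. At moderate odds ratios (1.5/2) the gain is under 1 point, and without balance the crude test is not conservative.

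Third, the plan already fits a model with both factors. This stands only in part, because that model is specified by treatment received. Running it by randomised arm would meet most of the point.

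A reader might infer that the primary result would be invalid, or that false positives would rise. Neither follows: in every scenario the crude test holds its level approximately or falls below it. A reader might also infer that power is certain to be lost and that the planned interval is too wide. The documents give no stratum-specific rates and specify no interval for the primary comparison, so they support only the conditional statement.

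**Conclusion.** The point holds as a minor one. The plan stratifies randomisation on two factors and then leaves them out of every comparison by randomised arm. At 67 per group, using them adds about 0 to 2.5 points of power one-sided (the side used for sizing) and up to about 3 to 3.5 points two-sided. The risk-difference interval narrows by 0 to about 4%. These figures assume odds ratios no larger than 2 for sex and 4 for dependence, independence of the two factors, near 1:1 balance within strata, abstinence of 65% and 80%, and that chi2 is the intended test. If the strata are weakly prognostic the gain is about nil. The gap between 62% and the intended 80% power comes from the sample size, and stratifying does not close it.

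**What to change.** In Results analysis plan, item 2, name the primary analysis: 12-month abstinence by randomised arm, intention to treat, using a Cochran-Mantel-Haenszel test stratified by sex × dependence (low versus moderate/severe), with the Mantel-Haenszel risk difference and its 95% confidence interval. Report the crude chi2 as supportive. State whether the test is one- or two-sided, and how allocation is balanced within strata.

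A logistic regression by randomised arm with these two factors is an acceptable alternative test. It is not interchangeable as an estimate: its conditional odds ratio is a different estimand, and its interval need not be narrower.

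The cost is one sentence. Both factors must be recorded in order to randomise, so no further data or patients are needed. The downside is at most about 1 point of power if the strata turn out not to be prognostic. As the trial is open-label, the choice should be fixed before outcome data are examined.
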